## Study Assessments

The primary endpoint of LAP117314 is the proportion of subjects experiencing diarrhoea with a severity of Grade 2 and above, as defined by the NCI CTCAE, version 4.03. The frequency and severity of episodes of diarrhoea will be recorded at each visit, by completion of the AE modules in the eCRF. Action taken as a result of diarrhoea (anti-diarrhoeal medication, unscheduled visits to healthcare professionals, dose reduction or

delay in treatment with lapatinib and capecitabine, treatment withdrawal, and intravenous fluid rehydration) will be recorded in the eCRF at each visit.

All subjects will complete the baseline DMD and FACIT-D during the 3 days prior to randomisation, before any study-related treatment is administered. Subjects randomised to receive octreotide will complete a second baseline DMD and FACIT-D before starting the first cycle of treatment with lapatinib and capecitabine. Subjects will then complete the DMD every week and the FACIT-D every 3 weeks until the end of 24 weeks of treatment with lapatinib and capecitabine or subject withdrawal, whichever is sooner. The DMD and FACIT-D will not be completed beyond 24 weeks of treatment.

Disease status will be assessed prior to the start of treatment with lapatinib and capecitabine in accordance with the Response Evaluation Criteria In Solid Tumours (RECIST), version 1.1. Disease progression will be evaluated by the investigator in accordance with local clinical practice during the course of treatment with lapatinib and capecitabine, and in accordance with RECIST version 1.1 at the end of study visit (subject withdrawal or at the end of 24 weeks of treatment with lapatinib and capecitabine, whichever is sooner). Treatment with lapatinib and capecitabine may continue beyond 24 weeks until disease progression occurs, but there will be no further data collection of disease progression beyond 24 weeks of treatment.

The safety and tolerability of treatment with octreotide, lapatinib and capecitabine will be evaluated by AE and serious AE reporting at each visit until subject withdrawal or the end of 24 weeks of treatment with lapatinib and capecitabine. Serious AEs and other specific safety assessments will be reported in subjects who continue treatment with lapatinib and capecitabine beyond 24 weeks. Serious AEs will be followed up until resolution or stabilisation of the event or until the subject is lost to follow-up.

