**Table 9 National Cancer Institute common terminology criteria for grading constipation adverse events**

Adverse Event Grade	Constipation
1	Occasional or intermittent symptoms; occasional use of stool softeners, laxatives, dietary modification, or enema
2	Persistent symptoms with regular use of laxatives or enemas; limiting instrumental ADL
3	Obstipation with manual evacuation indicated; limiting self care ADL
4	Life-threatening consequences; urgent intervention indicated
5	Death

ADL=Activities of daily living

Dose reductions and dose delays are permitted during treatment with lapatinib and capecitabine. The procedures to be followed are described in Section 5.10 for lapatinib and in Section 5.11 for capecitabine.

Study completion will be the end of 24 weeks treatment with lapatinib and capecitabine, or disease progression, unacceptable toxicity or subject withdrawal if this is sooner. Serious AEs and other safety data will be reported beyond 24 weeks in subjects who continue treatment with lapatinib and capecitabine until disease progression in countries where the Sponsor is supplying lapatinib and capecitabine. Serious AEs will be followed up until resolution or stabilization of the event or until the subject is lost to follow-up.

The efficacy of prophylactic octreotide in reducing the frequency and severity of diarrhoea is the primary endpoint of this study. Each episode of diarrhoea will be recorded by the investigator as an AE in the eCRF in accordance with the standard AE reporting procedure. Actions associated with the management of diarrhoea (use of anti-diarrhoeal medication, unscheduled visits to healthcare professionals, treatment interruption, rehydration) will be recorded in the eCRF.

Subjects will complete the DMD every week and the FACIT-D every 3 weeks during treatment with lapatinib and capecitabine to provide an additional perspective on the effects of treatment-associated diarrhoea.

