### 6.3. Treatment after Discontinuation of the 24 Week Study Treatment or Withdrawal from/Completion of Study

The investigator is responsible for ensuring that consideration has been given for the post-study care of the subject's medical condition whether or not GSK is providing specific post-study treatment.

In countries and centres where lapatinib and capecitabine are reimbursed and have been sourced locally, lapatinib and capecitabine should also be sourced locally for continuation

of treatment post-study. These subjects are considered to have completed the study after 24 weeks of treatment with lapatinib and capecitabine, and post-study care should be conducted in accordance with local best practice.

In countries and centres where lapatinib and capecitabine are provided by GSK, these drugs will also be provided by GSK for continuation of treatment post-study. After completing 24 weeks of treatment with lapatinib and capecitabine, these subjects will enter the long term follow up (LTFU) phase of the study and will continue to receive treatment with lapatinib and capecitabine until disease progression, unacceptable toxicity or death.

Upon discontinuation from treatment with lapatinib and capecitabine, subjects may receive additional (non protocol) anti-cancer therapy at the discretion of the treating physician. Every effort should be made to complete the required withdrawal evaluations and follow up evaluations relating to resolution or stabilization of SAEs prior to initiating further anti-cancer therapy or dosing of an investigational agent (see [Table 16](#) and [Table 17](#) for end of study and follow-up assessments and procedures).

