- Not mandatory at these visits, but should be conducted in accordance with local clinical practice, at the time of a scheduled 3 weekly visits when possible.
- PROs are the FACIT-D and the DMD.
- Week -1 baseline PROs to be completed prior to randomisation, before the octreotide 0.1mg s.c. tolerability assessment dose.
- If clinically indicated, in accordance with the Lapatinib SPC.
- First dose of octreotide LAR to be given 7 days before start of Cycle 1 treatment with lapatinib and capecitabine. Subjects must receive octreotide 0.1mg s.c. at least one hour before the first dose of octreotide LAR to assess tolerability.
- Visits at the start of Cycle 2 and Cycle 4 are mandatory.** Visits at the start of Cycle 3, 5, 6, 7 and 8 are not mandatory; visits every 3 weeks would be preferred, but may be adapted to match local practice.
- Week 0 baseline PROs to be completed before the first dose of lapatinib and capecitabine is administered.
- 
- Cycle 2 to be started 21 days ( $\pm 2$  days) after the start of Cycle 1. Other cycles should be started within  $\pm 4$  days of the 3 weekly treatment cycle intervals.
- Second dose of octreotide LAR to be given 28 days ( $\pm 2$  days) after first dose of octreotide LAR.
- After 24 weeks treatment with lapatinib and capecitabine. Investigators should continue to treat subjects with lapatinib and capecitabine beyond 24 weeks in accordance with local clinical practice.
- Serious adverse events and other safety data as described in Section 7.4 should be reported for all subjects who continue treatment with lapatinib and capecitabine beyond the 24 week end of study assessment.
- If more than 12 weeks since the screening cardiac function assessment.

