#### **7.1.9. Assessments after Study Completion: Long Term Follow Up**

Following completion of the 24 week study treatment period subjects may continue to receive treatment with lapatinib and capecitabine until disease progression or the occurrence of AEs leading to treatment discontinuation.

In countries and centres where lapatinib and capecitabine are provided by the study centre, subjects will continue to receive treatment with lapatinib and capecitabine in accordance with local practice. Post-study assessments of efficacy and safety will be performed in accordance with the local standard of medical care and the [Lapatinib](#) and [Capecitabine](#) SPCs.

In countries and centres where lapatinib and capecitabine are provided by GSK subjects will enter the LTFU phase of the study. Investigators will be required to collect and report the following safety information until lapatinib discontinuation:

- Adverse events (AEs) leading to lapatinib discontinuation.
- Other reasons leading to lapatinib discontinuation.
- Date of lapatinib discontinuation.

Additionally, investigators will be required to collect and report the following safety information, until 30 days following lapatinib discontinuation:

- Serious adverse events (SAEs) including AEs of special interest defined as SAEs will continue to be collected (as defined in Section [7.1.8](#) per protocol specific SAEs: cardiac, hepatic and pneumonitis).
- Pregnancies.
- Other AEs the investigator deems medically necessary to report.

Subjects with abnormal clinical or laboratory findings believed to be treatment-related will be followed until the condition resolves or until laboratory findings are not considered to be clinically significant.

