#### **7.4.7. Time Period and Frequency of Detecting AEs and SAEs**

The investigator or site staff is responsible for detecting, documenting and reporting events that meet the definition of an AE or SAE.

AEs will be collected from the time of treatment with the first dose of octreotide for subjects randomised to receive octreotide and treatment with the first dose of lapatinib and capecitabine for subjects randomised to receive no octreotide until 30 days following the end of the 24 week study period or discontinuation of study-related treatment, whichever is sooner, regardless of initiation of a new cancer therapy or transfer to hospice.

Serious AEs will be collected over the same time period as stated above for AEs. In addition, any SAE assessed **as related** to study participation (e.g., protocol-mandated procedures, invasive tests, or change in existing therapy), study treatment or GSK concomitant medication must be recorded from the time a subject consents to participate in the study up to and including any follow-up contact. All SAEs will be reported to GSK within 24 hours, as indicated in Section 7.4.9.

Serious AEs, AEs of special interest, AEs leading to treatment discontinuation and pregnancies will be collected for all subjects who enter the LTFU phase of the study (Section 7.1.9).

After discontinuation of study treatment, the investigator will monitor all AEs/SAEs that are ongoing until resolution or stabilization of the event or until the subject is lost to follow-up. At any time after 30 days the investigator may report any AE that they believe possibly related to study treatment.

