2.1.1 Data included in the analysis

All data up to the time of study completion (i.e. 24 weeks of lapatinib and capecitabine treatment) or withdrawal from the study will be included in the final analysis, regardless of duration of treatment.

All data with an assessment date or event start date (e.g. vital sign assessment date or start date of an adverse event) prior to or on the cut-off date will be included in the analysis. Any data

collected beyond the cut-off date will not be included in the analysis and will not be used for any derivations. For the final analysis the database lock date will be used as cut-off date.

All events with start date before or on the cut-off date and end date after the cut-off date will be reported as ‘continuing at the cut-off date’. The same rule will be applied to events starting before or on the cut-off date and not having documented end date. This approach applies, in particular, to adverse event and concomitant medication reports. For these events, the end date will not be imputed and therefore will not appear in the listings.

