5.1.3.2 Missing exposure end date imputation

In general, completely missing dates are not imputed. However, subjects completing 24 weeks of lapatinib and capecitabine may still be on lapatinib and capecitabine and so may have missing exposure end dates in their last dosing record. Missing exposure end dates for subjects who are still on lapatinib and capecitabine at the time of analysis will be imputed as the date of the End of Study/Withdrawal visit.

For subjects with missing exposure end dates at the time of data cut-off, i.e. for SRT summaries, the exposure end date will be imputed to be the earliest of: the date of the data cut-off, the date of End of Study/Withdrawal visit, or the death date. The imputed exposure end date will be used to calculate cumulative dose and exposure duration. The imputed exposure end date will be stored in the exposure analysis dataset and an exposure end date imputation flag variable will be derived indicating which exposure end date records are imputed. Imputed exposure end dates will also be stored on the study treatment end date variable.

For subjects who have missing end dates in their last exposure record because they are still on lapatinib and capecitabine, the on-therapy indicator variables (time in relation to lapatinib and capecitabine) are assigned to on-therapy for all records where the 'dataset'.date' is after or on the lapatinib and capecitabine start date.

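### The documents disagree on whose SAEs are reported after week 24, and the SAP's SAE and death tables have no common follow-up window

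*Protocol*

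**What the plan says.** **Collection, wider version.** The AE footnotes to Protocol Tables 16 and 17 point to Section 7.4 for the safety data concerned, SAEs among them, and say that these "should be reported for all subjects who continue treatment with lapatinib and capecitabine beyond the 24 week end of study assessment". SAP Tables 1-1 and 1-2 carry the same footnote. The Protocol Summary sets no limit by country: "Serious AEs and other specific safety assessments will be reported in subjects who continue treatment with lapatinib and capecitabine beyond 24 weeks".

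**Collection, narrower version.** Protocol 3.1 and SAP 1.1 restrict reporting beyond week 24 to subjects treated "until disease progression in countries where the Sponsor is supplying lapatinib and capecitabine". Of subjects with locally sourced drug, Protocol 6.3 says "These subjects are considered to have completed the study after 24 weeks of treatment with lapatinib and capecitabine". Protocol 7.1.9 reserves long-term follow-up (LTFU) for the rest: "In countries and centres where lapatinib and capecitabine are provided by GSK subjects will enter the LTFU phase of the study". Protocol 7.4.7 collects AEs and SAEs until "30 days following the end of the 24 week study period or discontinuation of study-related treatment, whichever is sooner", and after that only in LTFU subjects, apart from study-related SAEs and the follow-up of ongoing events.

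**Analysis.** SAP 2.1.1 opens by including data up to week 24 or withdrawal. It then includes everything dated up to the cut-off and adds: "For the final analysis the database lock date will be used as cut-off date". SAP 2.7 bases the safety summaries on all events collected in the study. SAP 2.7.4 tabulates all SAEs as number and percentage of subjects, and gives two death summaries: on-treatment deaths and all deaths.

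**The concern.** Two things go wrong together. A site with locally supplied drug, faced with an SAE at week 30, can cite the schedule footnote for reporting it and Sections 3.1, 6.3 and 7.4.7 for not doing so. Practice may then differ between sites with nobody in breach.

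The SAE and death percentages are cumulative proportions over the whole safety population, so they depend on how long each patient was observed. If some patients are observed to week 24 plus 30 days and others to progression, the percentage describes no particular period. It will also vary with the mix of drug supply among countries and centres. Safety and tolerability is a secondary objective, and these tables are its main summary.

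**Working it through.** No figure in the plan depends on this point, so there is nothing to reproduce. The check compares the texts and then estimates how many patients are affected.

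**1. Who is reported after week 24**

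| Place | Population |
|---|---|
| Protocol Tables 16 and 17, footnotes | all who continue |
| Protocol Summary | those who continue, no country limit |
| Protocol 3.1 | sponsor-supplied countries |
| Protocol 6.3 | locally supplied subjects have completed the study |
| Protocol 7.1.9 and 7.4.7 | LTFU subjects, i.e. sponsor-supplied |
| SAP 1.1 | sponsor-supplied countries |
| SAP Tables 1-1 and 1-2, footnotes | all who continue |

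Both documents contain both versions.

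**2. Which window the tables use.** Read literally, the first rule in SAP 2.1.1 would drop AEs from the 30 days after week 24, which Protocol 7.4.7 collects. The second rule admits LTFU events up to lock. SAP 2.1.3.10 defines on-treatment as first dose to last dose plus 28 days. One death summary uses that definition, but the SAE tables are not tied to it. It also follows each patient's own last dose, so it does not by itself give a shared length.

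**3. Lengths being mixed.** A locally supplied patient who completes week 24 is covered by Section 7.4.7 for 24 + 30/7 = 28.3 weeks from the first lapatinib dose. In the octreotide arm, collection opens 7 days earlier by design. A sponsor-supplied patient is covered until 30 days after stopping lapatinib.

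**4. How many could reach the disputed period.** Assume exponential progression, S(24) = 0.5^(24/median), with the medians in Protocol 1.1:
- 27.1 weeks (PFS, EGF100151): 0.5^(24/27.1) = 54.1%, or 33.6 of the 62 enrolled at the interim
- 28.6 weeks (PFS, EGF111438): 0.5^(24/28.6) = 55.9%, or 34.7 of 62
- 23.9 weeks (investigator-assessed time to progression, EGF100151): 0.5^(24/23.9) = 49.9%, or 30.9 of 62

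These are upper figures, because stopping for toxicity is ignored. Collection is in dispute only for the locally supplied patients among them.

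**5. Whether that period occurs.** The interim cut-off was 30 March 2016, and the DMC met on 9 September 2016, 163 days or 23 weeks later. If the interim trigger (at least 60 subjects through their 9-week assessment or discontinued) was met at the cut-off, the subjects behind it who were still on treatment were at least 9 + 23 = 32 weeks into lapatinib and capecitabine by then, with lock still to come.

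**6. Illustration of size (assumed inputs).** Take a median of 27.1 weeks, so μ = ln 2/27.1 = 0.0256 per week, and a constant SAE hazard λ while on treatment. Then P(T) = λ/(λ+μ) × [1 − exp(−(λ+μ)T)]. Setting P(24) = 20% gives λ of about 0.0127 per week. P(T) is then 25% at week 36, 28% at week 48 and 31% at week 76. Mean treatment time within 24 weeks is 17.9 weeks. With 12 to 52 weeks of later follow-up, captured treatment time rises by 0% if no patients are sponsor-supplied, 16% to 43% if half are, and 31% to 87% if all are.

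**The case against.** The best defence is that the footnotes defer to Section 7.4, and 7.4.7 sets a clear rule. It stands in part: the protocol does define a collection window, so calling follow-up undefined would be wrong. It does not remove the conflict. The pointer says which data to report, while the footnote itself names the wider population, and Section 3.1 makes adherence to the schedules mandatory.

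A reader might infer that the SAP simply pools everything up to lock. It does not say that. SAP 2.1.1 opens with the 24-week limit, Protocol 9.3.5 says the same of the summaries, and the lock date can be read as an outer bound. The supportable finding is that the SAP gives two rules and its SAE tables follow neither explicitly.

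A reader might also infer a safety bias between arms. Supply is set by country or centre and allocation is 1:1, so none is shown. Chance imbalance is possible with about 31 per arm (62 split equally, an assumption), since no stratification by country is described. The SAP plans no inferential safety comparison.

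Finally, a reader might infer from SAP 5.1.3.2 that deaths on drug after week 24 would be labelled post-treatment. The rule reads "Missing exposure end dates for subjects who are still on lapatinib and capecitabine at the time of analysis will be imputed as the date", and the date meant is that of the end-of-study visit. It covers only missing end dates of subjects still on drug at analysis, which a patient who has died is not. A recorded stop date in LTFU leaves nothing to impute. The same section counts later records of such subjects as on-therapy, and its cut-off rule takes the death date into account. That inference is not supported.

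**Conclusion.** The point holds in two parts. Both documents contradict themselves on whose SAEs are reported after week 24. The SAP also fixes no common window for its SAE and all-deaths tables, so the absolute percentages can blend about 28 weeks of observation with observation to progression according to drug supply.

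It would be too strong to say that half the trial is in dispute. Under exponential progression, about 50% to 56% is a ceiling on patients continuing past week 24, and only the locally supplied part of that group is disputed for collection. The documents do not give that part, so it could lie anywhere from none to all of the ceiling. The rise from 20% to 25%–31% is an illustration under a constant hazard and should not be read as a forecast. The defect affects how absolute safety rates are interpreted. It should be corrected, but it does not undermine the trial's comparison of arms.

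**What to change.** 1. Reconcile the footnotes to Protocol Tables 16 and 17, the Protocol Summary, and SAP Tables 1-1 and 1-2 with Protocol 3.1, 7.1.9 and 7.4.7, so that one rule governs SAE reporting after week 24.
2. In SAP 2.1.1, replace the two data limits with one statement. In SAP 2.7 and 2.7.4, restrict the by-arm AE, SAE and death tables to the window every patient shares under Protocol 7.4.7: first dose to 30 days after week 24 or discontinuation, whichever is sooner. Align the 28-day on-treatment definition in SAP 2.1.3.10 with it.
3. Put later LTFU SAEs and deaths in a separate table by arm, with the number of patients followed.

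The cost is some footnote wording, one date filter in the safety programs and one extra table. Late events leave the main tables but remain reported. The SAP was written after recruitment had stopped, so rewording cannot standardise what sites have already done. The SAP window and the separate table therefore matter most, and both can be settled before database lock.

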**Table 17 Time and events schedule; Subjects who receive no octreotide**

	Screen 	Lapatinib and Capecitabine Cycle		Withdrawal from Study Treatment or End of Study Visit 
		Cycle 1	Cycle 2  to 8	
Procedures				
Informed Consent	x			
Inclusion/Exclusion Criteria	x 	x		
Demographics	x			
Medical/Surgical and Treatment History	x			
Efficacy and Safety Assessments				
AE/Toxicity Assessment		x	x	x 
Disease Assessment	x 	(x) 	(x) 	x
PROs 		x 	x	x
Concurrent Medications	x	x	x	x
Physical Exam	x			x
Dermatological Exam	x	(x) 	(x) 	x
Weight, Height, Vital Signs (Temp, BP, pulse)	x			x
ECOG Performance Status	x 			x
Cardiac function	x			x 
ECG	x			(x) 
Lab Assessments				
Liver function	x	(x) 	(x) 	x
Pregnancy Test	x			x
Study Treatments				
Dispense Lapatinib and Capecitabine		x	x	
Assess Lapatinib and Capecitabine Returned			x	x

- Schedules for screening assessments are presented in Section 7.1.1 and Section 7.1.2. All screening and baseline assessments must be completed prior to the start of Cycle 1 of treatment with lapatinib and capecitabine.
- Inclusion and exclusion criteria are presented in Section 4.1.2 and Section 4.1.3, and other considerations are presented in Section 4.2. Investigators must ensure all subjects are eligible to receive treatment with lapatinib and capecitabine in accordance with the Lapatinib SPC and Capecitabine SPC, including evaluation of cardiac function.
- Disease assessment criteria are described in Section 7.1.11.
- ECOG status may be assessed more than once prior to randomisation, but only the assessment within 3 days prior to randomisation will be recorded in the eCRF.
- Not mandatory at these visits, but should be conducted in accordance with local clinical practice, at the time of a scheduled 3 weekly visits when possible.
- PROs are the FACIT-D and the DMD.
- Week 0 baseline PROs to be completed prior to randomisation, before the first dose of lapatinib and capecitabine is administered.
- If clinically indicated, in accordance with the Lapatinib SPC.
- 
- Cycle 2 to be started 21 days ( $\pm 2$  days) after the start of Cycle 1. Other cycles should be started within  $\pm 4$  days of the 3 weekly treatment cycle intervals.
- Visits at the start of **Cycle 2 and Cycle 4 are mandatory**. Visits at the start of Cycle 3, 5, 6, 7 and 8 are not mandatory; visits every 3 weeks would be preferred, but may be adapted to match local practice.
- After 24 weeks treatment with lapatinib and capecitabine. Investigators should continue to treat subjects with lapatinib and capecitabine beyond 24 weeks in accordance with local clinical practice.

13. Serious adverse events and other safety data as described in Section 7.4 should be reported for all subjects who continue treatment with lapatinib and capecitabine beyond the 24 week end of study assessment.
14. If more than 12 weeks since the screening cardiac function assessment.

